5.5 Drug Accountability

The Investigator is responsible for maintaining accurate study drug accountability records throughout the study.

Each dispensing of study drug will be documented in the eCRF.

The Investigator is responsible for ensuring all unused medication is destroyed at the investigational site following the appropriate drug accountability procedures.

5.6 Compliance

The study drug is administered intravenously at the study site, so it is not necessary to monitor patient compliance with the study drug regimen.

5.7 Previous and Concomitant Medications

Concomitant medication or therapy which is considered necessary for the patient's welfare and which will not interfere with the study medication, may be given at the discretion of the Investigator. There are no prohibited medications in this study.

Concomitant medications and therapies will be recorded from screening to D30. Administration of all concomitant drugs and therapies must be reported in the appropriate section of the eCRF along with the minimum and maximum dose levels administered (if applicable). Recording of dates of administration/therapy for chronic treatment and actual dates of administration of all acute concomitant medication is required.

Additionally, section 5.8 provides guidelines for concomitant medications to be administered for certain medically-expected AEs for this particular study population.

If a patient is discharged from the hospital prior to D30, the patient must be instructed that the Investigator should be informed about additional medication up to D30.

Patients in this study will be managed with supportive care measures according to the best clinical practice established locally in each ICU.

5.8 Guidance on medications to be administered/patient management for expected Adverse Events

Recombinant Human IFN beta-1a has been widely used in man for the treatment of multiple sclerosis and is considered safe. Some adverse effects are anticipated. Most common are changes in blood biochemistry of liver function, i.e. ALAT, ASAT, AFOS. A slight elevation in liver enzymes is often seen, and needs to be followed. These changes usually subside after cessation of treatment. Most common severe adverse effects are fever, tachycardia and rigor, since the drug substance is to some extent pyrogenic by nature. These adverse effects mostly occur shortly after administration and cease after treatment. These adverse effects may be managed with otherwise suitable medication depending on the symptom: paracetamol or other antipyretics for fever, beta blockers for tachycardia, benzodiazepines for rigor or even propofol sedation in the ICU setting.

Few adverse effects are expected after the treatment period since, as shown in the FPCLI001 study, FP-1201 activity decreases significantly within few days after administration, according to MxA measurements. Thus, the IMP will be washed out before discharge from the hospital. For more information on the anticipated effects of the FP-1201-lyo treatment see the **Investigators' Brochure**.

6 VARIABLES AND METHODS OF ASSESSMENT

The timing of the assessments of the variables is shown in the Schedule of Procedures (Tables 5, 6 and 7).

6.1 Efficacy Variables

The following efficacy variables will be assessed:

- Mortality assessments
- Ventilator free days (VFDs)
- ICU free days
- Organ failure free days
- Days in hospital and/or other health care facility
- Days on haemodialysis
- Prevalence of abdominal compartment syndrome as measured by intra-abdominal pressure (IAP)

6.2 Methods and Timing for Assessing, Recording and Analysing Efficacy Parameters

6.2.1 *Mortality assessments*

The following mortality assessments are to be conducted:

- All-cause mortality at D30 and D90 (3 months)
- Kaplan-Meier survival curve to D90

Mortality is to be captured by assessing whether the patient is alive or dead and by recording the date of death and reason/diagnosis leading to death when available.

6.2.2 *Disability assessment*

Modified ranking scale (mRS) at D0 and D90 will be used to evaluate study subject disability. Single mRS value is applied for every patient based on patient or caregiver interview (Table 9). Pre-operation D0 mRS value is collected for reference (possible to collect also retrospectively by interview).

6.2.3 *Ventilator free days (VFDs)*

The number of VFDs at D30 will be assessed.

Definition of VFDs to D30:

VFDs to D30 is defined as the number of calendar days after initiating unassisted breathing (UAB) to D30 from first treatment, assuming a patient survives at least 48 consecutive hours after initiating UAB.

For example: If a patient initiates UAB on D16 and survives to D30, that patient would be assigned a VFD value of 14. If a patient initiates UAB on D16 but dies on D25 he/she would be assigned a VFD value of 9. If a patient survives for more than 48 hours after initiating UAB but then requires assisted breathing (for any reason) before D30 then the VFD value would be the total number of UAB days before D30 unless a period of assisted breathing was less than 24 hours and the purpose of

assisted breathing was a surgical procedure. Patients who die without initiating UAB will be assigned a VFD value of zero. All patients, whether still on or already off positive pressure ventilation, who are transferred to another hospital or healthcare facility prior to D30, will be followed up to assess the VFD outcome at D30.

Patients transferred to other health care facilities or to another hospital prior to D30 while still receiving assisted breathing/without assisted breathing will be followed until D30 to assess this efficacy measure. Unassisted breathing (UAB) is defined as any of the following:

- spontaneous breathing with face mask
- nasal prong oxygen or room air
- t-tube breathing
- tracheostomy mask breathing
- CPAP < 5 without pressure support (PS) or IMV assistance
- use of CPAP or BIPAP solely for sleep apnoea management

6.2.4 ***ICU free days***

The number of ICU free days will be assessed at D30.

Definition of ICU free days:

ICU free days are defined as the number of days from the time of ICU discharge to D30 after the first dose of study medication, assuming survival for at least two consecutive calendar days after ICU discharge and continued stay outside the ICU setting to D30. If a patient returns to the ICU and subsequently needs ICU admission to D30, ICU free days will be counted from the end of the last period of ICU discharge to D30. A period of ICU admission lasting less than 24 hours in relation to a surgical procedure is considered an ICU free day. If a patient is held at the ICU at D29 or dies at the ICU prior to D30, ICU free days will be zero. Patients transferred to another hospital or other health care facility will be followed until D30 to assess this endpoint.

6.2.5 ***Organ failure free days***

Organ failure free days are assessed at D30.

Definition of organ failure free days:

Organ failure free days are defined as the number of days in the first 30 days after the first dose of study medication that the patient is alive and free of organ failure with a SOFA score of zero for the following six organ parameters: respiration, coagulation, liver, cardiovascular, CNS and renal function (refer to the SOFA score illustrated in Table 1).

The total SOFA score and the individual elements of the SOFA score are assessed daily from baseline to D30 if the patient is in the ICU and have an arterial catheter (or is on the ward but have an arterial catheter suitable for PaO₂/FiO₂ assessment), include:

- a) PaO₂/FiO₂ (mmHg)
- b) platelets × 10³/mm³
- c) bilirubin (mg/dl)
- d) hypotension
- e) GCS (an estimation will be used for sedated patients)

f) creatinine (mg/dl)

Refer to Table 8 for the SOFA assessment schedules.

Patients who die without achieving a SOFA score of zero will be assigned an organ failure free days value of zero.

Table 1: The SOFA score

SOFA score	0	1	2	3	4
Respiration					
PaO ₂ /FiO ₂ , mmHg	>400	>300 ≤400	>200 ≤300	>100 ≤200 with respiration support	≤100
Coagulation					
Platelets × 10 ³ /μl	>150	>100 ≤150	>50 ≤100	>20 ≤50	≤20
Liver					
Bilirubin, mg/dl (μmol/L)	<1.2 (<20)	≥1.2 <2.0 (≥20 <33)	≥2.0 <6.0 (≥33 <102)	≥6.0 <12.0 (≥102 <204)	≥12.0 (≥204)
Cardiovascular					
Hypotension ^a	No hypo tension	MAP <70 mmHg	Dopamine ≤5 or dobutamine (any dose)	Dopamine >5 or epinephrine ≤0.1 or norepinephrine ≤0.1	Dopamine >15 or epinephrine >0.1 or norepinephrine >0.1
Central nervous system					
Glasgow Coma Scale ^{b, c}	15	13 14	10 12	6 9	<6
Renal					
Creatinine, mg/dl or μmol/l or urine output	<1.2 <110	≥1.2 <2.0 ≥110 <171	≥2.0 <3.5 ≥171 <300	≥3.5 <5.0 ≥300 <440 or <500 mL/d	≥5.0 ≥440 or <200 mL/d

^a Adrenergic agents administered for at least 1 hour (doses are given in μg/kg/min).

^b For patients who are intubated, the verbal response is scored as:

5 – Seems able to talk

3 – Questionable ability to talk

1 – Generally unresponsive.

^c For patients who are sedated use an estimated score for GCS (the assumption is 15, if no other factors than sedation affect GCS)

Abbreviations: MAP=mean arterial pressure; PaO₂/FiO₂=partial pressure of oxygen/fraction of inspired oxygen; SOFA=Sequential Organ Failure Assessment.

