7.5.1 Schedule of assessments for D0 to D5

Day 0 0 hrs and post dose:

The first dose of study medication will be administered on D0 at 0 hrs (with maximum of 4 hours after the RAAA surgery). The following D0 study medication administration procedures and post dose assessments are performed (refer to Table 5) and the data is recorded in the eCRF:

- Administration of study medication: FP-1201-lyo or placebo, administered as a bolus intravenous injection, followed by a 5 ml flush of sterile saline
- SOFA score assessment for baseline
- Recording of concomitant medications and therapies
- AE reporting commences after the consent has been obtained.

Day 1 to Day 5:

From D1 to D5 inclusive, the following study assessments and procedures will be performed (patient will not be subjected for additional invasive assessments if not standard for patient care in ICU/hospital ward):

- Check if patient is on ventilation (refer to VFD definition in Section 6.2.3)
- Check if patient is in the ICU

- Check if patient is on organ support
- The number of organ failure free days by means of SOFA. SOFA scores are assessed daily in the ICU (refer to Table 1 and Table 8 for the SOFA composition and schedules. **Note:** The worst daily value of each element should be used to calculate the overall SOFA score.
- Vital signs (temperature, BP and HR) must be measured and recorded between 6 am to 10 am using the values closest to 8 am (assuming these values are representative of the patient's condition). All vital signs assessments must be made at the same time point when possible.
- Blood biochemistry: samples must be taken between 6 am to 10 am (refer to Section 6.3.2. for specific biochemistry variables)
- Haematology: samples must be taken between 6 am to 10 am (refer to Section 6.3.2. for specific haematology variables)
- Intra-abdominal pressure (IAP) must be measured daily between 6 am to 10 am during ICU stay or until complete resolution of elevated pressure. Not applicable if abdomen was left open at index operation
- Daily recording of major surgical outcomes affecting patient
 - open abdomen: yes/no (to detect time of closure or re-opening)
 - lower limb embolization (yes/no), consequent rhabdomyolysis (yes/no)
 - Explorative laparotomy for bleeding (yes/no), record blood loss
 - Explorative laparotomy and bowel resection (yes/no)

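### The organ-failure-free-day definition has no organ-support rule, so some haemodialysis days and some ventilated, sedated days are counted as free of organ failure

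*Protocol*

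**What the plan says.** Protocol 6.2.5 defines an organ-failure-free day as one on which the patient is "alive and free of organ failure with a SOFA score of zero for the following six organ parameters". Those six cover the lungs, clotting, the liver, the circulation, consciousness and the kidneys. The section refers to Table 1 for scoring and then lists the elements assessed daily. The renal entry in that list is "f) creatinine (mg/dl)", with no urine output. Table 1 scores the renal item on creatinine "or urine output".

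In Table 1, respiratory support appears only at the low end of the respiration row ("≤200 with respiration support"). A score of 0 needs PaO2/FiO2 above 400, with no condition on ventilation. Footnote c deals with GCS in sedated patients: "the assumption is 15, if no other factors than sedation affect GCS". Section 7.3 requires the worst value of each element on the day.

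The only special case in 6.2.5 is a patient who dies without reaching SOFA zero, who gets zero days. SAP 12.2 adds that the count is analysed as a proportion of days with a SOFA score and compared by the Mann-Whitney test. Neither document mentions dialysis or ventilation in this definition, although both are recorded. Section 7.5.1 has an item "Check if patient is on organ support" and a matching ventilation check for D1 to D5, and 7.5.2 repeats both for D6 to D30.

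**The concern.** The trial's title names prevention of multi-organ failure, and this secondary endpoint is the one that sums failure across organs. A SOFA item measures physiology as it stands, and support can bring that physiology into the normal range. Dialysis lowers creatinine, and ventilation can hold the oxygenation ratio up. Without a support rule, a day on which an organ's function is being replaced can be recorded as a day without organ failure.

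Two consequences follow. First, the trial's endpoints can describe one patient-day in conflicting ways: as a day on haemodialysis (6.2.7) or not ventilator-free (6.2.3), and also as free of organ failure. Second, the SAP's denominator is the number of days with a SOFA score, which 6.2.5 and 7.3 largely restrict to ICU or arterial-line days. With a short denominator, one such day moves a patient's proportion noticeably. If a patient has 10 SOFA days (an assumption), it moves by 1/10 = 10 percentage points and puts that patient above everyone at zero in the rank test.

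**Working it through.** The plan states no figure here to reproduce. The check is to score hypothetical days with Table 1 as printed. All patient values are illustrative assumptions. Unless stated otherwise: PaO2/FiO2 420, platelets 200, bilirubin 0.8 mg/dl, MAP 80, no adrenergic agent, GCS 15, creatinine 1.0 mg/dl.

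Rules applied: respiration is 0 if PaO2/FiO2 >400 and 1 if >300 to 400. Platelets score 0 if >150 and 1 if >100 to 150. CNS is 0 at GCS 15 and 4 below 6. Renal is 0 if creatinine <1.2 mg/dl, but 3 if urine is <500 mL/d and 4 if <200 mL/d, when urine output is used. Norepinephrine up to 0.1 scores cardiovascular 3. A day is free only if the six scores sum to 0.

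| Day | Resp | Plt | Liver | CV | CNS | Renal | Sum | Free? |
|---|---|---|---|---|---|---|---|---|
| A. Ventilated, sedated, GCS taken as 15 | 0 | 0 | 0 | 0 | 0 | 0 | 0 | Yes |
| A2. As A, scored on an observed GCS of 3 | 0 | 0 | 0 | 0 | 4 | 0 | 4 | No |
| B. Dialysis, urine 1000 mL/d | 0 | 0 | 0 | 0 | 0 | 0 | 0 | Yes |
| C. Dialysis, urine 100 mL/d, Table 1 renal item | 0 | 0 | 0 | 0 | 0 | 4 | 4 | No |
| C2. As C, creatinine only (6.2.5 list) | 0 | 0 | 0 | 0 | 0 | 0 | 0 | Yes |
| D. Dialysis, ventilated, sedated, urine 1000 mL/d | 0 | 0 | 0 | 0 | 0 | 0 | 0 | Yes |
| E. As A, norepinephrine 0.05 | 0 | 0 | 0 | 3 | 0 | 0 | 3 | No |
| F. As A, platelets 120 | 0 | 1 | 0 | 0 | 0 | 0 | 1 | No |
| G. Ventilated, PaO2/FiO2 350 | 1 | 0 | 0 | 0 | 0 | 0 | 1 | No |

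Days A, B and D show the gap. Days E, F and G show its limits: one non-zero item, including any listed adrenergic agent given for long enough ("Adrenergic agents administered for at least 1 hour"), removes the day. Days C and C2 are the same day under the two renal descriptions in 6.2.5, with opposite results.

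Daily urine output appears in none of these: the 6.2.5 list, Table 2, the flow charts, the visit lists in 7.4 and 7.5. The only diuresis named is during the procedure (6.4).

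Frequency: the documents give no input for it. Suppose 10–25% of patients are dialysed for 3–7 SOFA days, and the other five items are 0 on 5–20% of those days. If the renal item is always 0 and days are independent, the share of patients with at least one such day runs from 0.10 × (1 − 0.95³) = 1.4% to 0.25 × (1 − 0.80⁷) = 19.8%. If the renal item is 0 on a quarter of dialysis days, the range is 0.10 × (1 − 0.9875³) = 0.4% to 0.25 × (1 − 0.95⁷) = 7.5%. With days in a patient fully correlated as well, it is 0.10 × 0.0125 = 0.1% to 0.25 × 0.05 = 1.3%. Every input is assumed. A spread from 0.1% to 19.8% shows only that the frequency cannot be estimated from the plan.

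**The case against.** The endpoint is declared as SOFA-based, and ventilation and dialysis have secondary endpoints of their own, so organ support is reported. Different constructs may disagree on a day. Six items must be 0, each on its worst value, so a ventilated day needs every recorded PaO2/FiO2 above 400. Section 6.2.5 cites Table 1, whose urine criterion catches oliguric dialysis days. The eCRF is not among the documents, and 6.2.8 shows that ICU patients have a bladder catheter, so urine output may well be available. The GCS convention is disclosed, and it applies only when sedation alone lowers the score. The analysis is supportive and unadjusted for multiplicity, in a trial stopped after an interim on 35 evaluable patients.

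Most of this stands as a limit on scope. It does not close the gap, because days A, B and D pass every one of these conditions.

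A reader might go further and infer that the endpoint depends only on oxygenation, creatinine and an assumed GCS. It does not: platelets, bilirubin and the cardiovascular item must also be 0. A reader might also infer that the endpoint favours the arm with more dialysis. That would need a difference in dialysis use between blinded arms, and nothing in the documents shows one. Finally, an unsupported patient with creatinine 115 µmol/l scores renal 1 and is never free. That follows from the strict SOFA-zero threshold, and a support rule would not change it.

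**Conclusion.** The definition lacks an organ-support rule. When all other items are 0 on the worst daily value, it counts two kinds of day as free: a non-oliguric haemodialysis day with creatinine below 1.2 mg/dl (any such day if creatinine alone is scored), and a ventilated, sedated day with PaO2/FiO2 above 400 and GCS taken as 15. Separately, the 6.2.5 list and Table 1 disagree on the renal item, and this decides how oliguric dialysis days are classified.

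The conclusion rests on Table 1 as printed and on neither document adding a rule elsewhere. The number of affected days is unknown, and so is any effect on the comparison between arms. This is a validity gap in one supportive secondary endpoint. It does not touch the D30 mortality analysis or safety. It is worth correcting because the correction is cheap.

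**What to change.** In protocol 6.2.5 and SAP 12.2, state for this endpoint that:

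- a day on haemodialysis is not an organ-failure-free day, whatever the creatinine;
- a day on assisted breathing, as defined through 6.2.3, is not an organ-failure-free day, except for surgical ventilation of less than 24 hours, which 6.2.3 already exempts.

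Reconcile the 6.2.5 element list with Table 1 by saying whether the renal item uses creatinine alone or creatinine or urine output and, if the latter, where daily urine output is recorded.

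Derive the rule by merging the daily status data with the SOFA data (SAP Listings 16.2.14 and 16.2.24), with Listing 16.2.18 for dialysis. This assumes that status is held by day, as 7.5.1, 7.5.2 and the listing title indicate. D0 has a SOFA score but no organ-support check in 7.5.1, so name its source; 6.5 counts dialysis days from screening.

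Fix the rule before database lock. The current SAP was written after the first interim, for which protocol 5.4 has the randomisation code opened, so SAP section 15 should record the rule as a change made after that analysis. Keep the SOFA-only count as a sensitivity table.

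The cost is a short text change, one data merge and one extra table. The downside is slightly fewer organ-failure-free days, and patients ventilated only for airway reasons lose those days. The change concerns scoring only and implies nothing about treatment.

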6.2.6 Days in hospital and/or other health care unit

The length of a patient's hospital stay will be assessed by:

- the number of days the patient stayed in hospital at D30 and D90
- the number of days the patient stayed at another primary or rehabilitating health care unit after hospital discharge at D30 and D90.

6.2.7 *Days on haemodialysis*

The number of days on haemodialysis will be assessed at D30 and D90. Haemodialysis at D90 is considered permanent.

6.2.8 *Prevalence of compartment syndrome as measured by intra-abdominal pressure (IAP)*

Intra-abdominal pressure (IAP) is routinely measured during ICU stay via urine bladder catheter. IAP is recorded daily and a comparison of IAP between study groups is made.

6.3 **Safety Variables**

6.3.1 *Adverse Events*

6.3.1.1 *Collection of Adverse Events*

It is the responsibility of the Investigator to collect all AEs (both serious and non-serious) derived by observation, by spontaneous unsolicited reports of patients, and, where appropriate, by routine open questioning, e.g., “How have you felt since I last saw you?”

6.3.1.2 *Definitions*

Definitions of AEs and SAEs and their documentation and reporting within this study follow International Conference on Harmonisation (ICH) Good Clinical Practice, European Union, and national regulations and requirements (Clinical safety data management 1994).

An AE is defined as any untoward medical occurrence that occurs in a patient or clinical investigation subject administered a pharmaceutical product, and which does not necessarily have to have a causal relationship with this treatment. An AE can therefore be any unfavourable and unintended sign (including an abnormal laboratory finding), symptom or disease temporally associated with the use of an investigational product, whether or not it is considered related to the product.

All AEs up to D30 are collected. All AEs up to D30, which lead to death, are reported as SAEs. However, all deaths up to D90 will be reported as SAEs. Concomitant illnesses, which existed before entry into the study, will not be considered AEs unless there is any deterioration from baseline that is considered clinically relevant or significant during treatment or follow-up period until D30 or discharge from ICU. All AEs must be documented, regardless of the source of identification (e.g., physical examination, laboratory assessment, ECG, reported by patient).

Pre-existing conditions will be recorded in the eCRF on the Medical History or appropriate page.

A TEAE is defined as an AE that begins or that worsens in severity after at least one dose of study drug has been administered up to D30.

See 6.3.1.4 for the schedule of collection of adverse events

6.3.1.3 *Assessment of Adverse Events*

It is recognised that the patient population in the ICU will experience a number of common aberrations in laboratory values, signs and symptoms due to the severity of their underlying disease and the impact of standard therapies. These will not necessarily constitute an AE unless they require significant intervention, lead to discontinuation of blinded study drug or are considered to be of concern in the Investigator's clinical judgement.

Each AE will be assessed by the Investigator with regard to the following categories:

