6.3.1.3.4 Clinical Laboratory Adverse Event

Abnormal laboratory findings (e.g., biochemistry, haematology, urinalysis) or other abnormal assessments (e.g., vital signs) that are judged by the Investigator as clinically significant will, if certain requirements are met, be recorded as AEs or SAEs. Clinically significant abnormal laboratory findings or other abnormal assessments that meet the definition of an AE or SAE and are detected during the study, or are present at baseline and significantly worsen following the start of the study, will be reported as AEs or SAEs. However, clinically significant abnormal laboratory findings or other abnormal assessments that are associated with the disease being studied (unless judged by the Investigator as more severe than expected for the patient's condition), or that are present or detected at the start of the study and do not worsen, will not be reported as AEs or SAEs.

The Investigator will exercise their medical and scientific judgment in deciding whether an abnormal laboratory finding or other abnormal assessment is clinically significant.

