6.3.1.5 Reporting Serious Adverse Events

According to applicable European Union regulations and requirements, an SAE must be reported to the Sponsor from the trial site as soon as possible **within 24 hours** of becoming aware of the SAE. A medically qualified person at the trial site identified on the Delegation of Authority Log with this responsibility must assess the SAE. Any member of the clinical trial site staff can assist in reporting an initial SAE. The Principal Investigator or delegated sub-investigators are responsible for the SAE reporting procedures at the site during the trial, and must always sign-off on each SAE even if other site staff have reported the event on behalf of the investigators. A delegation log at each trial site will clearly show delegation of responsibilities regarding SAE reporting.

The SAE form must be completed with all the relevant information and forwarded to Crown Pharmacovigilance by:

- Email: [REDACTED]
- or*
- Fax: [REDACTED] In case of delivery failure, please **call:** [REDACTED]

If the SAE is urgently reported by telephone, a paper SAE form must always be completed and forwarded to Crown Pharmacovigilance as soon as possible.

The Investigator and the Sponsor (or Sponsor's designated agent) will review each SAE report and the seriousness and the causal relationship of the event to study treatment will be evaluated. In addition, the Sponsor (or Sponsor's designated agent) will evaluate the expectedness according to the reference document (Investigator Brochure). Based on the Investigator and Sponsor's assessment of the event, a decision will be made concerning the need for further action.

If consensus on the assessment cannot be reached between the parties (e.g., Investigator and Sponsor/Sponsor's delegate), all opinions will be provided in the Council for International Organizations of Medical Sciences Form I report and reporting to the CA and IEC should be based on the highest degree of causality provided.

Details for reporting SUSARs can be found in Section 6.3.1.7.

All SAEs will be recorded that occur between signing of informed consent and D30. Events occurring after D30 and coming to the attention of the Investigator should be reported only if they are considered in the opinion of the Investigator to be causally related to the investigational drug. However, all deaths up to D90 will be reported as SAEs.

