7.6 Discharge

7.6.1 Discharge prior to D30

If a patient is discharged from the operating hospital prior to D30 and not discontinued, a complete **final evaluation** should be made **at the day of discharge** as described below (refer to Table 7):

- Check if patient is on ventilation (refer to VFD definition in Section 6.2.3)
All patients, whether still on or already off positive pressure ventilation, who are transferred to another hospital or healthcare facility prior to D30 will be followed up to assess the VFD outcome at D30.
- Check if patient is in the ICU
Patients that are transferred to another hospital or healthcare ICU facility prior to D30 will be followed up to assess the days in ICU at D30.
- Check if patient is on organ support
- The number of organ failure free days by means of SOFA (arterial blood gas analysis should not be done if not part of standard care at this point).
- Physical Examination of major body systems
- Vital signs (temperature, BP and HR) must be measured and recorded between 6 am to 10 am using the values closest to 8 am (assuming these values are representative of the patient's condition). All vital signs assessments must be made at the same time point when possible.
- Intra-abdominal pressure (IAP) must be measured daily between 6 am to 10 am during ICU stay or complete resolution of elevated pressure
- Days on vasoactive drugs
- Recording of concomitant medications and therapies
- AE reporting
- Patient is invited for a laboratory visit to assess NABs and other D30 assessments on D30.
- Mortality follow-up: For all patients who withdraw from the study prior to D30, mortality will be assessed at D30 and D90 (3 months). **Note:** A time window of +14 days is given for D90 assessment.

In the case of an ongoing AE, appropriate safety evaluations and/or additional tests may be performed at any time when clinically indicated at the discretion of the Investigator, until resolution or D30, whichever is the sooner.

Any ongoing AEs should be followed up to resolution or study D30, whichever is the sooner.

If the patient refuses any of the above assessments or is lost to follow-up, this is noted in the eCRF.

If a patient is lost to follow-up, mortality data will be sought from alternate sources such as the patient's local physician or available national databases, whenever possible.

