13.1 Adverse events

All recorded adverse events will be coded according to the Medical Dictionary for Regulatory Activities (MedDRA). Treatment emergent adverse event (TEAE) is defined as an AE that begins or worsens in severity after at least one dose of study drug has been administered. Non-treatment emergent AEs are listed only.

TEAEs will be summarized using frequency and subject based tables. TEAEs will be tabulated by treatment group, system organ class (SOC), preferred term (PT), causality and severity. For analysis purposes, each subject will also be categorized by the maximum severity reported for a given TEAE and these will be tabulated by maximum severity. TEAEs will be summarized separately for treatment period (D1-D5) and short-term follow-up period (D6-D30). TEAEs are not collected, and therefore not reported, during the mid-term follow-up.

Serious adverse events (SAEs) and AEs leading to discontinuation will be summarized by treatment groups. All deaths up to D90 are reported as SAEs.

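### Protocol 6.3.1.2 stops counting worsening of a pre-existing illness at D30 or ICU discharge without saying which applies, and no other adverse-event rule carries an ICU limit

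*Protocol*

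**What the plan says.** Protocol section 6.3.1.2 (Definitions) states that an illness which existed before entry is not an AE unless it deteriorates from baseline in a way considered "clinically relevant or significant during treatment or follow-up period until D30 or discharge from ICU". Two stops are named, with nothing to say whether the earlier or the later applies.

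The other rules that fix what is counted, and until when, have no ICU limit:

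- Same paragraph of 6.3.1.2: "All AEs up to D30 are collected".
- TEAE definition, also in 6.3.1.2: an AE that "begins or that worsens in severity after at least one dose of study drug has been administered up to D30".
- Section 6.3.1.3.4, abnormal laboratory findings and other assessments: those that "are present at baseline and significantly worsen following the start of the study, will be reported as AEs or SAEs". The section exempts findings that belong to the disease under study, unless they are more severe than expected.
- Section 6.3.1.5: "All SAEs will be recorded that occur between signing of informed consent and D30". Deaths are reported as SAEs to D90.
- Section 6.5: AEs for the economic evaluation run from first dose to D30.
- SAP section 13.1: TEAEs are tabulated for the treatment period and again for D6 to D30.

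No section of either document reconciles the ICU-discharge wording with these.

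**The concern.** The rule in 6.3.1.2 decides whether worsening of an existing condition is an AE at all. The TEAE definition applies only to events already classed as AEs, so it inherits whatever 6.3.1.2 excludes, and the SAP's D6 to D30 tables cannot restore it.

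If a site takes the earlier stop, a chronic condition that worsens on the ward without meeting a seriousness criterion is not recorded. Another site that follows the general D30 rule records the same event. The protocol plans 10 to 18 sites, so the choice could vary within the trial.

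ICU discharge also comes after randomisation, and ICU-free days is itself an outcome (sections 3.2.3, 6.2.4 and 8.5.2). A counting window that closes at ICU discharge could therefore differ in length between the arms, and the counts would no longer compare like with like. Safety forms part of the primary objective (section 2.1).

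**Working it through.** **No stated figure to reproduce.** The point rests on the wording. The arithmetic below is an illustration on assumed inputs.

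**Step 1: the possible readings of the two stops.**

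| Reading | Window for worsening of a pre-existing illness | Fit with the other rules |
|---|---|---|
| Earlier stop | Closes at ICU discharge if that comes before D30 | Conflicts with the general D30 collection rule and with 6.3.1.3.4 |
| Later stop | Runs past D30 for a patient still in the ICU | Conflicts with the D30 end of the TEAE definition and with 6.3.1.4 and 6.3.1.5, which after D30 take only causally related events and deaths |
| The ICU words have no effect | To D30 | Consistent, but then the words serve no purpose |

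On each reading the ICU words either create a conflict or add nothing.

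**Step 2: an example of the conflict.** Suppose a liver enzyme is abnormal at baseline and rises significantly on D9, on the ward, and the exemption for the disease under study does not apply. Under 6.3.1.3.4 it is reported. Under 6.3.1.2 with the earlier stop, the same deterioration, taken as worsening of a pre-existing liver condition, is not an AE.

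**Step 3: how early the window could close.** Section 7 provides for patients who leave the ICU during the treatment period. Section 3.1 allows treatment to stop early only if the patient no longer needs the ICU and the investigator also judges further treatment unlikely to help. So on the earlier-stop reading the window could close before D5, possibly while dosing continues.

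**Step 4: what a cut at ICU discharge would do to the counts.** Assumptions, none of them in the documents: a constant rate r of qualifying deterioration per patient-day, the same in both arms; ICU stay of t days; no allowance for deaths. The proportion of patients with a counted event is

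P(t) = 1 − exp(−r × t)

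For r = 0.01, P(5) = 1 − exp(−0.05) = 4.9%, P(10) = 1 − exp(−0.10) = 9.5%, and P(30) = 1 − exp(−0.30) = 25.9%. The full set is:

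| Assumed r per day | Counted, 5 vs 10 ICU days | Ratio | Counted, 8 vs 10 ICU days | Ratio | Ratio, 10 vs 10 | Common window to D30, both arms |
|---|---|---|---|---|---|---|
| 0.005 | 2.5% vs 4.9% | 0.51 | 3.9% vs 4.9% | 0.80 | 1.00 | 13.9% |
| 0.01 | 4.9% vs 9.5% | 0.51 | 7.7% vs 9.5% | 0.81 | 1.00 | 25.9% |
| 0.02 | 9.5% vs 18.1% | 0.52 | 14.8% vs 18.1% | 0.82 | 1.00 | 45.1% |

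Two effects are visible. Events are missed in both arms even when ICU stays are equal: at r = 0.01 and 10 ICU days, 9.5% are counted against 25.9% to D30. A difference between arms appears only if ICU stays differ, and it follows whichever arm stays longer. If the 5 and 10 days are exchanged, the ratio at r = 0.01 is 1 / 0.5125 = 1.95. With one window to D30 the counted proportions are equal when the true rates are equal.

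**The case against.** A reader might infer more: that the plan cuts AE counts at ICU discharge and so flatters the active arm. The case against that reading is strong.

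- **The cut is not stated.** Elsewhere the protocol says explicitly when the earlier of two stops applies, for example "Any ongoing AEs should be followed up to resolution or study D30, whichever is the sooner" in section 7.6.1, and similarly in section 4.4.1. Section 6.3.1.2 contains no such words, so the earlier stop is one reading among several.
- **The general collection rules point to D30.** An investigator who follows 6.3.1.4, 6.3.1.5 and Table 6 would go on recording AEs on the ward.
- **The scope is narrow.** Only worsening of pre-existing illness is touched; new-onset AEs run to D30 on any reading. Serious ward events have their own route through the SAE rules to D30, and deaths to D90.
- **The TEAE sentence is not a competing rule for pre-existing illness.** It does not count every worsening, only that of events already classed as AEs.
- **The direction of any bias is open.** Under section 6.2.4 a patient who dies in the ICU before D30 scores zero ICU-free days, so more ICU-free days can come from fewer deaths and not from shorter stays. The design assumes 37% mortality on placebo and 15% on active (section 8.2). Patients saved from death could stay longer in the ICU and be observed for longer.

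All of this stands, and it rules out a claim of demonstrated bias. It leaves the inconsistency in place. The absence of an explicit earlier-stop rule shows that the sentence is ambiguous, and the other rules show that the ICU words do not fit.

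**Conclusion.** The inconsistency is real and specific. One sentence in 6.3.1.2 brings in ICU discharge as a stop, and no other AE rule in the protocol or SAP carries one. If sites took the earlier stop, non-serious ward deterioration of pre-existing illness went unrecorded and is missing from the TEAE tables, whether or not ICU stay differed by arm.

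A distorted comparison between arms needs two further conditions: the earlier-stop reading and unequal ICU stays. The documents establish neither. They give no ICU stay by arm and no rate of deterioration, so the ratios of about 0.51, 0.80 to 0.82 and 1.00 show only how the mechanism would work under the assumed inputs. The conclusion that the active arm gains a safety advantage is not supported.

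**What to change.** In section 6.3.1.2, delete the last four words of the phrase quoted above, so that deterioration of a pre-existing illness counts as an AE up to D30 for every patient, whenever the patient leaves the ICU. This matches the TEAE definition and the SAE window, removes the conflict with 6.3.1.3.4, and fits the D6 to D30 tables in SAP section 13.1. A matching line in the eCRF completion instructions is needed. The cost is a few more ward AEs to record.

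The SAP reports that the study was discontinued after the first interim analysis, so the edit alone cannot change what was collected. The study report should state which window the sites applied to worsening of pre-existing illness. The SAP still places steps before database lock; if that point has not passed, ward records can be queried where possible for deteriorations up to D30 that were left out.
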